- m. Baseline eye examinations may be performed at any time during the Screening period. Eye exams at Week 4, Week 8, Week 13, Week 26, Week 39, Week 52, Week 56 and/or Early Termination are required only if eye-related signs or symptoms are reported by the subject or observed by the investigator. If a subject experiences a treatment-emergent eye abnormality, an eye examination inclusive of slit lamp and near and far visual acuity testing should be performed by a qualified ophthalmologist or optometrist within 24 to 48 hours of event onset or on the next business day after symptom onset to evaluate the abnormality.
- n. Hematology and coagulation parameters include hemoglobin, MCV, MCHC, hematocrit, platelet count, RBC count, WBC count with differential, ANC, and PT, aPTT, INR, and fibrinogen. See also [Table 5](#).
- o. Liver aminotransferases include AST and ALT. Liver aminotransferases collected as part of the clinical chemistry panel for safety are also applicable for efficacy assessments.
- p. Fasting clinical chemistries include chloride, carbon dioxide, sodium, potassium, glucose, BUN, calcium, magnesium, creatinine, albumin, ALT, AST, ALP, GGT, total bilirubin, indirect and direct bilirubin, and total protein. CPK (total and fractionated) is to be reported at Screening and at Baseline. See also [Table 5](#).
- q. Urinalysis includes specific gravity, pH, blood, glucose, protein, ketones, and microscopic examination of sediment, if present. See also [Table 5](#).
- r. Subject contact to reliably assess medication use between visits is encouraged around Week 10, Week 17, Week 23, Week 30, Week 34, Week 43, and Week 47. See Section 9.7 for a list of accepted and excluded concomitant medications. If a subject receives a vaccine, including the COVID-19 vaccine, details regarding that vaccine should be recorded as a concomitant medication(s), including manufacturer, dose, and dates of each injection. Any vaccine-related reactions should be recorded as described in Section 12.2.
- s. The same biopsy samples will be used for histology analysis by the central study pathologist and by digital pathology.

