5.2. Safety

The safety endpoints are:

- Adverse events (AEs) throughout the study.
- Electrocardiograms (ECGs) at Weeks 26 and 52.
- Vital signs at each study visit.
- Physical examination findings at each study visit.
- Eye examination findings at each study visit.
- Hematology and coagulation results at each study visit.
- Liver aminotransferase levels at each study visit.
- Clinical chemistry results at each study visit.
- Urinalysis results at each study visit.

- Pregnancy test results throughout the study.
- Prior and concomitant medications throughout the study.
- Results of anthropometric measurements at Week 52.

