7. GENERAL DATA HANDLING CONSIDERATIONS

All analyses will be conducted using SAS software Version 9.4 or higher.

All data in the database will be presented in by-subject data listings. Unless otherwise stated, all listings will be sorted by treatment group, center ID, subject number, and assessment date and time, if available.

Unless stated otherwise, continuous data will be summarized by treatment group using descriptive statistics including number of subjects (n), mean, median, standard deviation (SD), first quartile (Q1), third quartile (Q3), minimum (min) value, maximum (max) value.

Unless stated otherwise, categorical data will be summarized by treatment group using counts and percentage based on the number of non-missing values. For selected summaries, the number of missing values will be presented as a separate category with no percentage, if one or more subjects have missing data. Counts of zero will be presented without percentages.

Descriptive statistics will be presented with the following numerical precision:

- Minimum and Maximum: same as the raw data collected
- Mean, Median, Q1, and Q3: one additional decimal place to that reported for Minimum and Maximum
- SD: two additional decimal places than the Minimum and Maximum
- Percentages: reported to one decimal place if percent is <100. If the value is 100, no decimal place will be reported.

Unless otherwise noted, statistical inference will be based on two-sided testing with a 5% significance level. Confidence intervals will be at the 90% and 95% levels.

P-values will be reported to four decimal places. If the value is below 0.0001 it will be noted as < 0.0001; if the value above 0.9999 it will be noted as > 0.9999.

All data up to the time of study completion/withdrawal from the study will be included in the analysis, regardless of duration of treatment.

Numbering for data displays will be based on [International Council for Harmonization \(ICH\) E3](#) whenever possible.

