7.9. Multiple Assessments and Visit Windows

Nominal visits (e.g., those identified by the study eCRF) will be the basis of summarization and statistical analysis; no visit date windowing will be conducted. Unless specified otherwise, data from unscheduled visits will be included in: (1) summaries of most extreme and baseline data, (2) summaries of specific abnormalities at any time post-baseline, (3) adverse events and any other summaries not based on study visit, (4) subject data listings, and (5) analyses that utilize MRI-PDFF, PK, lipidomic/metabolic biomarkers, collagen/fibrous area and fibrosis score assessed by digital pathology, SNPs relevant for NASH, and PRO-C3 data where unscheduled visit results may be used in analyses at the closest scheduled visit; if the closest scheduled visit already has valid MRI-PDFF data then the unscheduled visit results will not be used in the analysis.

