10.2. Clinical Laboratory Evaluations

Clinical chemistry, hematology, coagulation, and urinalysis parameters will be reported based on conventional units as applicable. The following laboratory evaluations will be reported in data summaries:

- Chemistry: Chloride, Sodium, Blood urea nitrogen, Creatinine, Albumin, Total protein, AST, GGT, Total bilirubin, Indirect and direct bilirubin, Carbon dioxide, Potassium, Calcium, Magnesium, Glucose, Alkaline phosphatase, ALT, Creatine phosphokinase (total and fractionated) (screening and baseline only). Note that AST and ALT collected as part of the clinical chemistry panel are also applicable for efficacy assessments.
- Hematology: Hematocrit, Hemoglobin, Red blood cell count, MCV, Platelet count, White blood cell count with differential, Absolute neutrophil count, MCHC.
- Coagulation Studies: Prothrombin time, Fibrinogen, Activated partial thromboplastin time, international normalized ratio (INR).
- Urinalysis: Specific gravity, Protein, pH, Ketones, Blood, Microscopic examination of sediment, Glucose.

Observed values and changes from baseline for laboratory evaluations will be summarized at each visit and will also include the most extreme change from baseline. The percent change from baseline at each visit and the most extreme percent change from baseline will also be summarized. Select laboratories mean change from baseline by study visit will be depicted graphically in a longitudinal line plot with standard error of the mean.

Laboratory data will also be summarized in shift tables of baseline to most extreme change based on range categories of low (below lower limit of normal [LLN], normal, and high [above upper limit of normal [ULN]]. Urinalysis results and shifts will be based on the categories present in the data.

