10.3. Vital Signs

Vital signs include oral temperature, pulse (bpm), systolic and diastolic blood pressure (mmHg), and respiration rate (breaths/minute). Note that systolic and diastolic blood pressure will be summarized with the other anthropometric parameters. Observed values and changes from baseline for vital signs will be summarized at each visit and time point, as well as for most extreme change from baseline.

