10.4. Electrocardiogram (ECG)

Electrocardiogram (ECG) parameters include HR (bpm), PR (ms), QRS (ms), QT (ms), QTcF (ms), and RR interval (ms). Observed values and changes from baseline for ECG parameters will be summarized by treatment group at each visit and time point.

Investigator reported ECG result will be tabulated by visit and worst-case post-baseline. In addition, the shifts from baseline to each visit and worst-case post-baseline will be summarized. Worst case post-baseline will be based on the worst observed value on or after the treatment start date. Categories will include within normal limits, abnormal without clinical significance, and abnormal with clinical significance.

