10.5. Ophthalmologic Examinations

The proportion of subjects experiencing ophthalmologic abnormalities will be tabulated by visit and by treatment group. The clinical interpretation of the ophthalmologic examination will be tabulated as normal or abnormal. The worst-case post-baseline will also be summarized.

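### SAP 10.5 does not pair eye examinations with each subject's own baseline, so its normal/abnormal tables cannot separate old abnormalities from new ones

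*SAP*

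**What the plan says.** SAP 5.2 lists "Eye examination findings at each study visit" among the safety endpoints. SAP 10.5 gives the whole analysis in three sentences: the proportion of subjects with ophthalmologic abnormalities by visit and arm, a worst post-baseline summary, and the classification rule, "The clinical interpretation of the ophthalmologic examination will be tabulated as normal or abnormal". It mentions no shift, no restriction to subjects normal at baseline, and no category for new or worsened findings.

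A baseline result exists for pairing. Footnote m to the Schedule of Assessments (Protocol Table 2) states: "Baseline eye examinations may be performed at any time during the Screening period". The same footnote and Protocol 12.1.4 require later examinations only when eye signs or symptoms are reported or observed.

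The neighbouring sections do compare with baseline:

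- Laboratory data (SAP 10.2): "Laboratory data will also be summarized in shift tables of baseline to most extreme change".
- Vital signs (SAP 10.3): "Observed values and changes from baseline for vital signs will be summarized at each visit and time point".
- ECG (SAP 10.4), after tabulating the investigator's result by visit and worst case: "In addition, the shifts from baseline to each visit and worst-case post-baseline will be summarized".

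Physical examinations (SAP 10.6) are only listed.

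**The concern.** A subject may enter the trial with an eye examination already read as abnormal. If that subject is re-examined and the same abnormality is still there, the SAP 10.5 tables count the subject as abnormal after baseline. Nothing in the table distinguishes this subject from one whose eye was normal at screening and became abnormal on treatment.

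At stake is the readability of one descriptive safety display. Eyes are of interest for this drug: Protocol 5.2 reports dry eye as the most common treatment-emergent event on TVB-2640 in the China cohort (8 of 21 treated), so the display is likely to be read closely.

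**Working it through.** **Step 1. Compare the safety sections.**

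| Measurement | By visit | Worst or most extreme | Compared with own baseline |
|---|---|---|---|
| Laboratory (SAP 10.2) | yes | yes | change and shift |
| Vital signs (SAP 10.3) | yes | yes | change |
| ECG result (SAP 10.4) | yes | yes | shift to each visit and to worst case |
| Eye examination (SAP 10.5) | yes | yes | none stated |
| Physical examination (SAP 10.6) | listing only | – | – |

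The ECG result and the eye examination have the same structure: a categorical interpretation shown by visit and as worst case. Only the ECG section adds the shift. SAP 7.6 does not fill the gap, because it defines change from baseline as a subtraction or a percentage, and neither applies to a normal/abnormal result.

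**Step 2. Can an old abnormality enter the count?** Exclusion criterion 29 (Protocol 8.2) removes clinically significant dry eye and corneal abnormality. The slit lamp examination in Protocol 12.1.4 also covers eyelids, conjunctiva, anterior chamber, iris and lens. A non-corneal abnormality can therefore be present at entry and persist.

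**Step 3. Would a baseline column be enough?** No. Under SAP 7, "categorical data will be summarized by treatment group using counts and percentage based on the number of non-missing values". The baseline percentage would cover essentially everyone, while later percentages would cover only subjects examined because of signs or symptoms. The two describe different groups, and only pairing within subjects separates old from new.

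**Step 4. Size.** The plan gives no figure to reproduce and no baseline abnormality rate. The following only shows how the display behaves under assumed inputs. Among re-examined subjects, let

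- p0 = share abnormal at baseline (assumed 10% to 40%),
- s = chance that the old finding is still recorded (assumed 50% to 100%),
- n = rate of new findings, independent of old ones (assumed 30% or 60%).

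Displayed abnormal rate = p0[s + (1 − s)n] + (1 − p0)n = n + p0·s·(1 − n).

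Share of abnormal entries that are old findings only = p0·s·(1 − n) / [n + p0·s·(1 − n)].

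If p0 and s are equal in both arms, the displayed arm difference = (1 − p0·s) × the difference in new findings.

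| p0, s | p0·s | Arm difference kept | Old only, n = 30% | Old only, n = 60% |
|---|---|---|---|---|
| 10%, 50% | 0.05 | 95% | 0.035/0.335 = 10% | 0.02/0.62 = 3% |
| 20%, 100% | 0.20 | 80% | 0.14/0.44 = 32% | 0.08/0.68 = 12% |
| 40%, 100% | 0.40 | 60% | 0.28/0.58 = 48% | 0.16/0.76 = 21% |

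The range is wide because every input is assumed. Equality between arms is also an assumption: re-examination follows signs or symptoms after randomisation, so randomisation does not secure it. The model treats a single examination, while the worst case may span several.

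**The case against.** The strongest reply is that old and new are already separated where it matters clinically. SAP 10.1 makes a clinically significant abnormal finding after the start of treatment an adverse event when it represents a change from baseline, and medical history if it came before. Protocol 12.2.1.1 counts worsening of a pre-existing condition as an adverse event. Eye disorder events are tabulated by preferred term (SAP 10.1) and by subgroup (SAP 7.2). SAP 10 has all safety data listed by subject, so a reviewer can pair the examinations by hand. All of this stands, and it is why the point is minor. It does not close the gap. An unchanged pre-existing abnormality is not an adverse event but still counts as abnormal in SAP 10.5, and a listing is not a summary of a declared endpoint.

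Three further replies limit the claim:

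- The eCRF field and table shells are not available, and SAP 10.5 does not define what it means to experience an abnormality. The missing shift is certain; mixing of old and new findings is possible but not shown.
- Many examinations may be unscheduled, since a treatment-emergent eye abnormality is to be examined within 24 to 48 hours or on the next business day. SAP 7.9 admits unscheduled results to "1) summaries of most extreme and baseline data, (2) summaries of specific abnormalities at any time post-baseline", and not generally to by-visit tables. The issue may therefore sit mainly in the worst-case summary.
- Examination triggered by symptoms limits any arm comparison more than the missing pairing does, and a shift table does not remove that selection.

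**Conclusion.** The point holds as a minor gap in a descriptive table. SAP 10.5 leaves out the within-subject baseline comparison that SAP 10.4 specifies for a result of the same kind. Non-corneal abnormalities that persist from screening would be counted with new ones, to an extent the documents do not allow anyone to estimate.

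A reader might go further and infer that the eye tables will in fact be dominated by old findings, or that the arm contrast will be diluted by a known amount. The documents do not support either: the percentages in the working rest wholly on assumed inputs and run from negligible to substantial. A reader might also infer that the dry eye signal would be hidden. That does not follow, because exclusion 29 removes clinically significant dry eye at entry, so carry-over should be least for that signal, and eye disorder adverse events have their own tables.

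The conclusion itself needs none of the assumed rates. It rests on the wording of SAP 10.5, the existence of a baseline examination, and a slit lamp examination whose scope is wider than the exclusion.

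**What to change.** In SAP 10.5 add one table by arm that shifts from baseline (normal/abnormal) to worst post-baseline result (normal/abnormal/not re-examined).

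- State that unscheduled examinations are included, in line with SAP 7.9.
- Show the number re-examined out of the Safety population.
- Add a footnote that re-examination is triggered by signs or symptoms, so the arm contrast is descriptive only.

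This follows the method that SAP 10.4 already uses for ECG. It uses data already collected, needs no extra examination, and leaves the error rate and sample size untouched. The cost is a few lines of SAP text and one extra table. A binary shift will not show an abnormal eye getting worse; that remains with the adverse event tables and the listings.

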10.6. Physical Examinations

Physical examination results will be presented in subject data listings.

11. CHANGES TO THE PLANNED ANALYSES

The following changes were made to analyses specified in the protocol. Any additional changes to the planned analyses as detailed in this SAP will be described in the CSR.

- Co-primary objectives and endpoints were added.
- Added 'To evaluate the effect of TVB-2640 50 mg QD compared with matching placebo on resolution of steatohepatitis and no worsening of liver fibrosis (by NASH CRN fibrosis score). Resolution of steatohepatitis is defined as absence of fatty liver disease or isolated or simple steatosis without steatohepatitis and a NAS of 0 or 1 for inflammation, 0 for ballooning, and any value for steatosis at Week 52.' as a secondary objective and endpoint.
- Added 'To evaluate the effect of TVB-2640 50 mg QD compared with matching placebo on histological improvement (decrease) at Week 52 in NAS by ≥ 2 points.' as a secondary objective and endpoint.
- Removed 'To evaluate the effect of TVB-2640 50 mg QD compared with matching placebo on fibrosis as assessed by ≥ 1 stage of fibrosis improvement by NASH CRN score without worsening of NAS (defined as no increase in any component of NAS) at Week 52.' as a secondary objective and endpoint.
- Added proportion of MRI-PDFF $\geq 50\%$ responders, MELD, and Agile3+ endpoints.
- Region (North America or not North America) was removed as an effect in all analyses.

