Analysis of the primary efficacy endpoint: The primary efficacy endpoint is the proportion of subjects experiencing either a histological improvement at Week 52 in NAS (ie, ≥ 2 points improvement in NAS with ≥ 1 point improvement in ballooning or inflammation) and without worsening of fibrosis (by NASH CRN fibrosis score), **OR** resolution of steatohepatitis and no worsening of liver fibrosis (by NASH CRN fibrosis score). The treatment groups will be compared based on the primary efficacy endpoint using a one-sided Cochran-Mantel-Haenszel (CMH) test stratified by the randomization stratifications T2DM status (yes or no), region (North America or not North America), and amount of fibrosis (F2 or F3) at the 0.05 significance level (where a higher responder proportion is a better outcome) and will be based on the Intention-to-Treat (ITT) population. The response Clopper-Pearson 90% and 95% confidence intervals (CI) will be derived for each treatment group.

A sensitivity analysis employing a logistic regression will be used to examine the robustness of the CMH results (see details described in the statistical section, below).

A subject who discontinues treatment prior to Week 42, does not provide a histological assessment on or after Week 42, or who otherwise has missing data will be considered a non-responder.

Further sensitivity analysis of the primary efficacy endpoint will employ multiple imputations for binary data. Pertinent details are included in the statistical analysis plan (SAP).

Analysis of the secondary efficacy and pharmacodynamics endpoints: The analysis of the secondary efficacy endpoints will be based on the ITT population. The imputation mechanism used in the analysis of the primary efficacy endpoint will also be adopted where applicable.

The analysis of the secondary efficacy endpoints of a categorical nature will be analyzed in a manner similar to the primary efficacy endpoint.

For the continuous secondary endpoints such as change from Baseline and percent change from Baseline, the Wilcoxon rank-sum test will be used to compare the treatment groups. For the continuous secondary endpoints, an analysis of covariance (ANCOVA) model will also be used with change from

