4.2. Randomization and Blinding

This will be a double-blind, randomized study. Subjects will be centrally assigned to randomized study treatment using an Interactive Web-based Response System (IWRS).

Approximately 162 unique subjects with liver fibrosis stage F2-F3 will be enrolled and randomized (2:1 ratio) to receive TVB-2640 50 mg or placebo (approximately 108 for TVB-2640 50 mg and approximately 54 subjects for placebo) PO QD for 52 weeks. Dynamic allocation is used for the randomization, stratified by T2DM status (Yes, No), region (North America, not North America), and amount of fibrosis (F2 or F3).

All subjects, Investigators, the Sponsor, and the clinical research organization (CRO) will be blinded to the treatment assignment of each individual subject. Members of the IDMC and the IDMC's independent statistician will be unblinded to treatment assignment as needed. In addition, specific vendors whose role in study conduct requires them to be unblinded (e.g., personnel operationally associated with the IWRS) may also be unblinded.

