7.1. Stratification and Covariates

Subjects will be randomized to achieve a 2:1 ratio of TVB-2640 50 mg to placebo, with the randomization stratified three factors: T2DM status (Yes, No), and amount of fibrosis (F2 or F3). Selected statistical models and tests will be stratified based on the randomization strata. Details on the models and tests are provided in the relevant sections below.

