9. EFFICACY

9.1. Primary Efficacy Endpoint Analyses

9.1.1. Principal Analysis of the Primary Efficacy Endpoints

The principal efficacy analyses will be conducted on the ITT population. Additional sensitivity and supplementary analyses will be performed for the primary efficacy endpoints, as described in the next section.

The treatment groups will be compared based on the primary efficacy endpoints using one-sided Cochran-Mantel-Haenszel (CMH) tests stratified by the randomization stratifications T2DM status at baseline (yes or no) and amount of fibrosis at baseline (F2 or F3).

Mathematically, the null and alternative hypotheses for the primary efficacy endpoints are stated as:

$$H_0: p_T \leq p_p$$

$$H_a: p_T > p_p$$

Where, p_T is the proportion of responders in the TVB-2640 50-mg treatment group and p_p is the proportion of responders in the placebo treatment group. The higher responder proportion is a better outcome.

A Clopper-Pearson 90% and 95% CI will be derived for each treatment group, and the stratified CMH odds ratio (with its 90% and 95% CI, using the control group as a reference group) will be produced to assess the treatment effect magnitude. The difference in treatment groups response rates will be provided and also be characterized by the 90% and 95% CIs using Miettinen and Nurminen (1985).

Subgroup analyses of the primary efficacy endpoints will be performed to assess whether the treatment effect is concordant among subgroups. The planned subgroup analyses are described in Section 7.2. Analyses will be performed if there is an adequate number of subjects in each subgroup.

A subject who discontinues treatment prior to Week 42, does not provide a histological assessment on or after Week 42, or who otherwise has missing data will be considered a non-responder.

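### The SAP drops region from every analysis although randomisation is balanced on it; if region is prognostic, the primary test becomes mildly conservative, and no reason is given

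*SAP*

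**What the plan says.** **Randomisation.** Protocol 7.1 and 9.6 and SAP 4.1 and 4.2 agree on three factors. SAP 4.2: "Dynamic allocation is used for the randomization, stratified by T2DM status (Yes, No), region (North America, not North America), and amount of fibrosis".

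**Protocol analysis.** In the synopsis the primary CMH analysis is "stratified by the randomization stratifications T2DM status (yes or no), region (North America or not North America), and amount of fibrosis (F2 or F3"), and Protocol 13.2.1 repeats this. The logistic sensitivity model in 13.2.1 and the ANCOVA in 13.2.2 also include region.

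**SAP analysis.** In SAP 9.1.1 the CMH analysis is "stratified by the randomization stratifications T2DM status at baseline (yes or no) and amount of fibrosis at baseline (F2 or F3"). The logistic model in 9.1.2 and the ANCOVA and MMRM models in 9.2 have no region term. Section 11 declares the change: "Region (North America or not North America) was removed as an effect in all analyses".

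**Description of the strata.** SAP 7.1 has subjects allocated "with the randomization stratified three factors: T2DM status (Yes, No), and amount of fibrosis (F2 or F3"), which announces three factors and names two. SAP 9.1.1 presents the same two as if they were the full set of randomisation strata.

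**Checks on the change.** None of the four sensitivity approaches in 9.1.2 brings region back. Region is also absent from the subgroup table in 7.2.

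**The concern.** When allocation is forced to balance on a factor, outcome differences between levels of that factor contribute almost nothing to the variance of the treatment comparison. A CMH test that does not stratify on the factor still counts that variation as noise. If region predicts response, the standard error is too large for the design and the test rejects too rarely under the null. The odds-ratio interval is affected in the same direction.

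At stake are some lost precision on both co-primary endpoints and an unexplained departure from the Protocol's primary test, with no planned analysis to show whether it matters. The SAP's text is also inconsistent: a programmer cannot follow 4.2, 7.1 and 9.1.1 as if all three described the same randomisation strata.

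**Working it through.** **1. The plan's own sample size.** Inputs from SAP 4.3 and Protocol 13.5: 40% against 20%, one-sided 0.05, 80% power, 2:1 allocation, 18.5% dropout. Unpooled normal approximation:

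n(placebo) = (1.645 + 0.842)² × [0.2×0.8 + 0.4×0.6/2] / 0.2² = 43.3, rounded up to 44. With 88 on active the total is 132, with power 80.6%. Then 132 / (1 − 0.185) = 162, which matches the plan.

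**2. Analytic level when a balanced factor is omitted.** Let π be the share outside North America, d the difference in response rate between regions, and p = 0.20 the overall null response rate.

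R² = π(1−π)d² / [p(1−p)]; level = 1 − Φ(1.645 / √(1−R²)).

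Example, π = 0.5 and d = 0.30: R² = 0.25×0.09/0.16 = 0.141; 1.645/√0.859 = 1.774; level = 3.8%.

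**3. Simulated level.** N = 162, 2:1 minimisation on the three factors, one-sided CMH, 60,000 null trials per row (Monte Carlo SE about 0.09 points). Assumed: 60% with diabetes, 50% F3, neither affecting response, and a biased coin of about 0.85.

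| Outside North America | Region difference | Analytic, region omitted | Simulated, SAP (4 strata) | Simulated, Protocol (8 strata) |
|---|---|---|---|---|
| 20% | none | 5.00% | 4.74% | 4.65% |
| 20% | 10 points | 4.92% | 4.82% | 4.90% |
| 20% | 20 points | 4.66% | 4.51% | 4.75% |
| 20% | 30 points | 4.23% | 4.00% | 4.81% |
| 50% | 10 points | 4.87% | 4.59% | 4.76% |
| 50% | 20 points | 4.47% | 4.14% | 4.69% |
| 50% | 30 points | 3.80% | 3.61% | 4.78% |

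With no region effect both tests sit near 4.7%, so about 0.3 points of the shortfall below 5% is discreteness, not the omission of region. Extreme checks (20,000 trials) go lower: 3.2% at 38 points with an even split, and 2.7% at 50 points with 20% outside.

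**4. Control.** Under simple randomisation with a 30-point difference (20,000 trials), the four-stratum test had level 4.9% (20% outside) and 4.6% (50% outside), against 4.8% and 4.8% with eight strata. Most of the loss therefore comes from balancing on region and then ignoring it.

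**5. Power at 40% against 20%, all 162 analysed, SAP strata against Protocol strata.** 20,000 trials per setting, SE about 0.26 points:
- 20% outside, 20 points: 83.7% and 84.0%
- 50% outside, 20 points: 84.5% and 85.0%
- 50% outside, 30 points: 85.0% and 86.7%

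**6. The same question on the odds-ratio scale** (20,000 trials per setting):

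| Outside North America | Region odds ratio | Level, SAP / Protocol strata | Power, SAP / Protocol strata |
|---|---|---|---|
| 5% | 3 | 4.5% / 4.5% | 83.9% / 83.3% |
| 10% | 2 | 4.9% / 5.0% | 84.0% / 83.4% |
| 20% | 2 | 4.7% / 4.7% | 83.8% / 83.7% |
| 30% | 2 | 4.7% / 5.0% | 83.7% / 83.4% |
| 30% | 3 | 4.5% / 4.9% | 84.4% / 85.0% |
| 40% | 5 | 3.8% / 4.6% | 85.4% / 87.2% |

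A further run of the last row (10,000 trials) gave 3.8% / 4.8% and 85.4% / 87.7%. An odds ratio of 3 with 30% outside means response of roughly 14% and 33% in the two regions; an odds ratio of 5 with 40% outside means roughly 10% and 35%. At 5% outside, the four extra strata would hold on average 162×0.05/4 = 2 subjects each, which fits the absence of any gain there.

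**The case against.** The strongest reply is that the effect is conditional and usually small. The documents give no region mix and nothing on whether region predicts response. With few subjects outside North America or a moderate region effect, restoring region gains no power and can cost about half a point. That cost is not confined to the case where region is irrelevant. This stands, and it limits the size of the point.

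The change is also declared in Section 11, and SAP Section 2 requires approval before unblinding. That stands too. Declaring a departure does not explain it, however, and no planned analysis shows whether the result depends on it. Sparse region cells could be the motive, but the documents do not say so.

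A reader might infer that the primary test is invalid, that false positives are inflated, or that the trial is underpowered. None of these follows: the error is in the conservative direction, and simulated power exceeds 80% in every setting run. A reader might also suspect a data-driven change, since the SAP cites a September 2023 Protocol that still uses region. Nothing in the documents supports that.

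**Conclusion.** The point holds as a modest one. The SAP's primary test does not match the allocation it analyses, the departure from the Protocol is unexplained, and the SAP misdescribes the randomisation strata.

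If region is prognostic, the primary test is mildly conservative. The level is about 4.5 to 4.8% for moderate effects when a minority is outside North America, and 4.1% at a 20-point difference with an even split. It is 3.6 to 4.0% at a 30-point difference. Power lost is half a point or less in the moderate settings and about 2 points in the strongest. If region is not prognostic, nothing is lost by omitting it.

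These sizes rest on an assumed region mix, region effect and minimisation algorithm. The power figures take 40% and 20% as the response rates among all 162 randomised subjects. Coverage of the odds-ratio interval was not simulated; its direction follows from the same mechanism. Whether the Miettinen-Nurminen interval for the rate difference should be stratified is a separate, minor matter.

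**What to change.** - **SAP 9.1.1 and 9.1.2:** restore region, using the value as randomised, as a CMH stratum and as a factor in the logistic model, as in Protocol 13.2.1. Add a rule, fixed before unblinding, for collapsing sparse region cells.
- **SAP 9.2 and 11:** restore region in the ANCOVA and MMRM models as well, then delete the Section 11 line. If 9.2 is left as it is, keep that line but limit it to those models; deleting it outright would turn a declared departure into an undeclared one.
- **SAP 7.1 and 9.1.1:** name all three factors in 7.1, and make the 9.1.1 description of the randomisation strata agree with 4.2.

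The cost is SAP wording and one more stratum variable. The statistical downside is up to about 0.5 to 0.8 power points if region is not prognostic, is weakly prognostic, or has few subjects outside North America. If the sponsor prefers to leave region out of the primary test, the minimum is a stated reason and a region-stratified sensitivity analysis, both in place before unblinding.
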